#### 1. OBJECTIVES

The main objective of this study is to collect long term safety and tolerability data in patients with myelofibrosis previously treated with ruxolitinib on protocol 2007-0169.

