#### 2.1 Rationale

Ruxolitinib is an inhibitor of the Janus kinases (JAKs) and is the only approved therapy for patients with myelofibrosis. Protocol 2007-0169 was a phase 1-2 study of ruxolitinib in these patients; now the therapy is approved and the protocol is closing. However, we plan to continue to monitor patients for long term safety and survival.

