#### 3. PATIENT ELIGIBILITY

#### 3.1 Inclusion Criteria:

 Currently enrolled in study 2007-0169 and benefiting from therapy as determined by treating physician,

- Eastern Cooperative Oncology Group (ECOG) performance status of 0, 1, or 2 at enrollment of this study,
- Ability and agreement to attend protocol-specified visits at the study site,
- Able to comprehend and willing to sign the informed consent form.
- Negative pregnancy test in females of childbearing potential. Male patients with female partners of child-bearing potential and female patients of childbearing potential are required to use two forms of acceptable contraception, including one barrier method, during their participation in the study and for 30 days following last dose. Acceptable forms of contraception include 1 highly effective method such as an intrauterine device (IUD), hormonal (birth control pills, injections, or implants), tubal ligation, or partner's vasectomy and at least 1 additional approved barrier method such as a latex condom, diaphragm, or cervical cap. Female patients of childbearing potential must not be breast-feeding or planning to breast feed and must have a negative pregnancy test ≤7 days before first study treatment.

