#### 4. TREATMENT PLAN

# 4.1 Starting Dose of Ruxolitinib and Treatment Cycle

Ruxolitinib has been developed for oral administration, a route of administration that is widely used and helps promote subject compliance to medication dosing. Both BID and QD regimens are permitted. Because of the short plasma half-life of ruxolitinib, there is little accumulation of ruxolitinib or active metabolites. The treatment period consists of multiple 28-day cycles, with subjects continuing in the study indefinitely as long as provided withdrawal criteria is not met, and there is continuing evidence of clinical benefit. Patients will continue therapy with ruxolitinib at the same dose and schedule as they have been receiving on study 2007-0169.

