#### 8. STATISTICS

#### 8.1 Study Population

All subjects who received at least one dose of study medication with at least one follow up assessment for safety will be included in the safety and tolerability analyses.

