#### **8.3 Adverse Events**

Severity of adverse events will be based on the NCI–CTCAE v3.0 (NCI Common Terminology Criteria for Adverse Events, Publ. Aug 9, 2006). The subset of adverse events that are considered by the Investigator to have a possible or probable relationship to study medication will be considered to be treatment-related adverse events. If the Investigator does not specify the relationship of the adverse event to study medication, the adverse event will be considered to be treatment-related. The incidence of adverse events and treatment-related adverse events will be tabulated.

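### Crude adverse event incidence, with no exposure time and no defined time origin, cannot show how risk changes with years on ruxolitinib, which is what a long-term safety study is for

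*Combined protocol and SAP*

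**What the plan says.** Section 1 gives the main objective as to "collect long term safety and tolerability data in patients with myelofibrosis previously treated with ruxolitinib on protocol 2007-0169". Section 2.1 adds that "we plan to continue to monitor patients for long term safety and survival".

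Section 3.1 admits patients who are "Currently enrolled in study 2007-0169 and benefiting from therapy as determined by treating physician", with ECOG "performance status of 0, 1, or 2 at enrollment of this study". Section 4.1 states that "Patients will continue therapy with ruxolitinib at the same dose and schedule as they have been receiving on study 2007-0169". Sections 4.1, 4.3 and 5.3 allow treatment to go on indefinitely while benefit lasts and no withdrawal criterion is met.

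Section 8.1 defines the safety set as "All subjects who received at least one dose of study medication with at least one follow up assessment for safety". Section 8.2 plans summary statistics such as means and frequencies. Section 8.3 says: "The incidence of adverse events and treatment-related adverse events will be tabulated". Section 8.4 compares laboratory values and vital signs with screening or baseline, without saying which study's baseline is meant. The only explicit start of a safety window is in section 7, where serious adverse events are captured from the first intervention under this protocol until 30 days after the last dose.

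**The concern.** A long-term safety question asks how risk behaves as years on drug accumulate. Three features of the plan stand in the way.

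- **Entry is mid-exposure.** The first dose under this protocol is not the first dose of ruxolitinib. The visit procedures in sections 5.1 and 5.2 do not list date of first dose or prior exposure, and section 8 does not use either.
- **Follow-up is open-ended.** A proportion of subjects with an event mixes risk with length of observation, and nothing in section 8 separates them.
- **The reference point is missing.** A shift from the 2007-0169 baseline and a shift from roll-over answer different questions. Section 5 describes no screening or baseline visit that would settle which is meant.

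At stake is whether the report can say that a given toxicity becomes more or less frequent with time on treatment. There is also a question of labelling. The population named in section 1 is wider than the one section 3.1 lets in, and no passage cautions against reading the results as those of everyone treated on 2007-0169.

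**Working it through.** The documents give no sample size, event rate, follow-up length or prior exposure, so there is no figure of the plan to reproduce. The three illustrations below rest on assumed rates.

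**1. Crude incidence against length of follow-up.** Assume a constant rate r per patient-year. The proportion with at least one event by time t is 1 − exp(−r·t).

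| r (assumed) | 0.5 years | 1 year | 3 years | 5 years |
|---|---|---|---|---|
| 0.05 | 2.5% | 4.9% | 13.9% | 22.1% |
| 0.10 | 4.9% | 9.5% | 25.9% | 39.3% |
| 0.20 | 9.5% | 18.1% | 45.1% | 63.2% |

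Within each row the risk is the same throughout; only observation time differs. The table also shows that 4.9% can come from a rate of 0.05 seen for 1 year or a rate of 0.10 seen for 0.5 years. Without the denominator the two cannot be told apart.

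**2. What person-time does.** With r = 0.10, expected time at risk per subject up to the first event or time t is (1 − exp(−r·t))/r.

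- At 0.5 years: 0.0488 events over 0.488 patient-years = 0.10.
- At 5 years: 0.393 events over 3.93 patient-years = 0.10.

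The rate is recovered at either length of follow-up. Splitting events and person-time by time since first dose would then show whether the rate moves with exposure.

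**3. Selection at entry.** Suppose half of those who start ruxolitinib have rate a and half have rate b for an event that ends treatment. After T years, the mean rate among those still treated is [a·exp(−a·T) + b·exp(−b·T)] / [exp(−a·T) + exp(−b·T)]; at first dose it is (a + b)/2. Example with a = 0.05, b = 0.20, T = 5: (0.05 × 0.7788 + 0.20 × 0.3679) / (0.7788 + 0.3679) = 0.1125/1.1467 = 0.0981, against 0.125 at first dose, a ratio of 0.78.

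| b (with a = 0.05) | T = 3 | T = 5 | T = 8 |
|---|---|---|---|
| 0.05 (homogeneous) | 1.00 | 1.00 | 1.00 |
| 0.10 | 0.98 | 0.96 | 0.93 |
| 0.20 | 0.87 | 0.78 | 0.68 |
| 0.40 | 0.63 | 0.45 | 0.31 |

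Selection alone could thus do nothing, or leave an observed rate at about a third of the starters' initial rate. This model holds each patient's risk constant. A risk that rises with cumulative exposure would push the other way. The documents supply no input that would choose among these cases.

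**The case against.** The best defence is that this is a descriptive, single-arm roll-over study with no hypothesis, comparator or target rate. Its restriction is stated openly in section 3.1. A roll-over study can follow only those still on treatment; events in patients who stopped earlier belong to 2007-0169. Describing this cohort is legitimate, and that part of the defence stands.

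It also rules out several stronger readings that a reader might infer:

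- **That the analysis counts time from roll-over.** Section 8.1 sets membership of the safety set, not a time origin, and no table by time on study is planned. Roll-over is a likely reading given the serious adverse event window in section 7, but it is not a stated rule. The defect is that the origin is unspecified.
- **That only patients who are benefiting are analysed.** Benefit is an entry condition. Subjects who later lose it remain in the safety set.
- **That the reported rates are biased low.** This needs a target of all patients who started on 2007-0169, which the protocol never states, and the direction is open even then.
- **That the median survival of 5 years in section 2 sizes the problem.** It is a general disease figure, while sections 2 and 2.4 say ruxolitinib improves survival. The fraction alive at roll-over is in any case not a bias in an adverse event rate.

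Two practical points also have weight. First-dose dates may already sit in the parent-study records, and the case report form specification is not among the documents. And since no sample size is given, yearly strata might be too thin to be useful.

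None of this supplies a denominator or a time axis. Even as a pure description of continuing patients, crude incidence over unequal, open-ended follow-up does not address long-term risk.

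**Conclusion.** The point holds as a gap in the analysis specification. Sections 8.2 and 8.3 cannot answer the study's own question, because incidence without exposure time mixes risk with length of observation: 4.9% against 39.3% at the same assumed rate of 0.10 per patient-year, for 0.5 and 5 years of follow-up. That conclusion does not depend on any selection bias. It rests on follow-up differing between subjects, which indefinite participation makes very likely. Prior exposure at entry probably differs too, although the documents do not give its length.

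The entry criteria mean that the results apply to patients still benefiting from ruxolitinib at roll-over. They may differ from those of all patients treated on 2007-0169, but the documents fix neither direction nor size. The ratios of 1.00 down to 0.31 above illustrate what selection alone can do on assumed rates; they are not estimates for this study.

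**What to change.** - **Data.** Record each subject's date of first ruxolitinib dose from 2007-0169.
- **Section 8.3.** Report adverse event rates per patient-year by time since first dose, with each subject entering the risk set at roll-over (delayed entry). Use bands wider than one year if numbers are small. The planned incidence table can stay beside this.
- **Section 8.4.** State whether baseline means the 2007-0169 baseline or the roll-over baseline, for shift tables and for change in vital signs.
- **Section 1 and the report.** Describe the population as patients still benefiting from ruxolitinib at roll-over.

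The cost is one extra date per subject, some added analysis and a narrower stated population. No visit, assessment or treatment rule changes.

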#### 2. BACKGROUND

Ruxolitinib (INCB018424 phosphate, JAKAFI™) is an inhibitor of the Janus kinase family of protein tyrosine kinases (JAKs). Ruxolitinib was approved in November 2011 for the treatment of patients with intermediate or high-risk myelofibrosis, including primary myelofibrosis, post-polycythemia vera myelofibrosis and post-essential thrombocythemia myelofibrosis. Ruxolitinib was approved in December 2014 for the treatment of patients with polycythemia vera who have an inadequate response to or cannot tolerate hydroxyurea.

JAKs play an important role in signal transduction following cytokine and growth factor binding to their receptors. In addition, JAKs activate a number of downstream pathways implicated in the proliferation and survival of malignant cells including the STATs (signal transducers and activators of transcription), a family of important latent transcription factors. Aberrant activation of JAKs has been associated with increased malignant cell proliferation and survival. In particular, a causal role for JAK2 has recently been suggested for the majority of patients with Philadelphia chromosome negative MPD.

The MPDs are a group of clonal hematologic diseases that include polycythemia vera (PV), essential thrombocythemia (ET), primary myelofibrosis (PMF) and post polycythemia vera/essential thrombocythemia myelofibrosis (post-PV/ET MF). MF may occur as a primary disorder or it may follow a preceding disease course with PV or ET. The clinical course in this disease is characterized by bone marrow fibrosis, hepatosplenomegaly, progressive anemia, extra medullary hematopoiesis, leukoerythroblastic peripheral blood findings and constitutional symptoms. Overall median survival is 5 years and causes of premature death include leukemic transformation, infections, thrombosis, cardiac failure, hepatic failure, respiratory failure and portal hypertension. For a small subset of patients who are young, otherwise healthy and have a histocompatible donor, allogeneic stem cell transplantation may provide a curative option, although a risk of significant mortality is associated with the procedure.

Ruxolitinib is the first treatment to increase the survival of patients with MF. A number of therapies may provide temporary symptomatic improvement or improvement in blood cell count, such as drugs (hydroxyurea, thalidomide, lenalidomide, danazol, prednisone), splenectomy, and involved field radiation at a site of extramedullary disease. None of these therapies have been approved as therapy for MF, and do not improve patients survival.

#### 2.1 Rationale

Ruxolitinib is an inhibitor of the Janus kinases (JAKs) and is the only approved therapy for patients with myelofibrosis. Protocol 2007-0169 was a phase 1-2 study of ruxolitinib in these patients; now the therapy is approved and the protocol is closing. However, we plan to continue to monitor patients for long term safety and survival.

#### 2.2 Formulation

Ruxolitinib will be provided by Incyte Corporation, as 5 mg and 25 mg strength tablets. The tablet formulation contains the active ingredient along with commonly used excipients. All excipients are of compendial grade.

#### 2.3 Ruxolitinib Potential Risks

The primary clinical risks with ruxolitinib treatment are the potential sequelae of decreased hematopoiesis, myelopoiesis, thrombopoiesis and decreased levels of circulating cytokines and growth factors, all of which are secondary to the inhibition of growth factor pathways by JAK2 antagonism.

The most frequently reported hematologic adverse reactions (any CTCAE Grade) are anemia, thrombocytopenia, and neutropenia. Increased rates of infection and anemia are potential risks of myelosuppression. Anemia can also lead to increase in number of transfusions. Hematologic parameters will be closely monitored for all subjects during this study, and therapy will be withdrawn or dosing held or reduced until resolution if there are clinically relevant declines.

#### 2.4 Ruxolitinib Benefits

Ruxolitinib has demonstrated marked reduction in spleen size in patients with MF, and without regard to presence of the JAK2 V617F mutation, as well as symptom reduction. Symptoms related to splenomegaly, as well as symptoms related to elevated cytokine levels, all show improvement with ruxolitinib treatment. After an initial small weight loss likely due to resolution of ascites and/or reduction in splenomegaly, there is an increase in total body weight; importantly, there is weight gain in subjects with low body mass index at entry, ie, cachectic subjects. Survival of patients on ruxolitinib is improved.

#### 3. PATIENT ELIGIBILITY

#### 3.1 Inclusion Criteria:

 Currently enrolled in study 2007-0169 and benefiting from therapy as determined by treating physician,

- Eastern Cooperative Oncology Group (ECOG) performance status of 0, 1, or 2 at enrollment of this study,
- Ability and agreement to attend protocol-specified visits at the study site,
- Able to comprehend and willing to sign the informed consent form.
- Negative pregnancy test in females of childbearing potential. Male patients with female partners of child-bearing potential and female patients of childbearing potential are required to use two forms of acceptable contraception, including one barrier method, during their participation in the study and for 30 days following last dose. Acceptable forms of contraception include 1 highly effective method such as an intrauterine device (IUD), hormonal (birth control pills, injections, or implants), tubal ligation, or partner's vasectomy and at least 1 additional approved barrier method such as a latex condom, diaphragm, or cervical cap. Female patients of childbearing potential must not be breast-feeding or planning to breast feed and must have a negative pregnancy test ≤7 days before first study treatment.

# 3.2 Exclusion Criteria:

- none

#### 4. TREATMENT PLAN

# 4.1 Starting Dose of Ruxolitinib and Treatment Cycle

Ruxolitinib has been developed for oral administration, a route of administration that is widely used and helps promote subject compliance to medication dosing. Both BID and QD regimens are permitted. Because of the short plasma half-life of ruxolitinib, there is little accumulation of ruxolitinib or active metabolites. The treatment period consists of multiple 28-day cycles, with subjects continuing in the study indefinitely as long as provided withdrawal criteria is not met, and there is continuing evidence of clinical benefit. Patients will continue therapy with ruxolitinib at the same dose and schedule as they have been receiving on study 2007-0169.

#### 4.2 Administration of Ruxolitinib

Subjects will self-administer the study medication, orally, in an outpatient setting every day in only one dose on daily schedule, and every 12 hours on twice a day schedule.

# 4.3 Duration of Therapy

Subjects may continue on therapy indefinitely as long as they are receiving clinical benefit based per investigator's criteria, and if they do not meet any of the withdrawal criteria (see section 5.5) and do not have disease progression.

## 4.4 Dosing Delays/Dose Modifications/Dose Interruptions

The course of management of the subject is at discretion of the investigator as determined in the best interest of the subject. For subjects who do not require dose interruption but have thrombocytopenia or neutropenia and no other serious safety concerns, strategy may vary case-by-case situation, to include one or more aspects of dosing schedule (ex. daily dose regimen, dosing interval, and frequency of dose or overall duration of administration of the therapy) as well as concomitant treatments to manage any untoward symptoms.

Mandatory dose decreases for safety reasons are dictated by platelet count levels. Dose modification strategies will be applied to all ongoing subjects enrolled in the study as per ruxolitinib's label (guidelines provided by FDA). When a decision is made to discontinue the subject or interrupt the therapy, then the recommendation is to consider instituting a tapering strategy based on the investigator's clinical judgment.

Utilization of a tapering strategy is based on condition of the subject, the current dosing regimen and the investigator's clinical judgment, and maintains a dose that has been shown to provide benefit to the subject or to increase the dose to a dose previously shown to provide benefit to the subject.

In any case, the following rules will ALWAYS apply:

- 1. The maximum dose must never exceed 25 mg BID, or if once-daily doses are used, dose may never exceed 100 mg QD.
- 2. Dosing must be interrupted with observation of a platelet count <25 x  $10^9$ /L.Dosing may be resumed with recovery of platelet count to a confirmed value of 35 x  $10^9$ /L or higher. Doses should be restarted at 5 mg BID, and may be increased by 5 mg BID every 2 weeks provided platelet count remains stable and exceeds 35 x  $10^9$ /L.
- 3. Dosing should be decreased by at least 5 mg BID increments with confirmed platelet count values of 25 x  $10^9/L$  to 35 x  $10^9/L$ . Dose increases may be instituted with recovery of platelets above  $50 \times 10^9/L$ .

Drug may be held up to 2 months for platelet or ANC abnormalities but if counts do not return to the level for reinstituting drug by that time, the subject will be discontinued from the study. Similarly, if drug is held for a non-hematologic toxicity for greater than two months, then the subject must be discontinued from the study.

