## 5.5 Criteria for Removal from the Study

Treatment with study drug is to be discontinued when any of the following occurs:

- Loss of therapeutic effect in the judgment of the Investigator
- Adverse event(s) that, in the judgment of the Investigator, may cause severe or permanent harm or which rule out continuation of study drug.
- Withdrawal of consent
- Lost to follow up
- Death
- Suspected pregnancy

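### Section 4.4 offers a taper when drug is to be stopped or interrupted but describes it as keeping or raising the dose, and does not reconcile this with Sections 4.3 and 5.5

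*Combined protocol and SAP*

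**What the plan says.** Section 4.4 introduces the taper in its second paragraph: "When a decision is made to discontinue the subject or interrupt the therapy, then the recommendation is to consider instituting a tapering strategy", at the investigator's judgment.

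The third paragraph is the only description of that strategy. It opens with the grounds for using it: "Utilization of a tapering strategy is based on condition of the subject, the current dosing regimen and the investigator's clinical judgment". The same sentence then says that the strategy "maintains a dose that has been shown to provide benefit to the subject or to increase the dose", the increase being to a level from which the subject benefited before.

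Three numbered rules follow, introduced by "In any case, the following rules will ALWAYS apply". Rule 1 caps the dose. Rule 2 states "Dosing must be interrupted with observation of a platelet count" below 25 x 10^9/L. Rule 3 calls for a reduction at confirmed counts of 25 to 35 x 10^9/L. The section closes with holds for platelet, neutrophil (ANC) or non-haematologic reasons, and with discontinuation from the study if a hold outlasts two months.

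Section 5.5 says "Treatment with study drug is to be discontinued when any of the following occurs" and lists six criteria. They include loss of therapeutic effect, suspected pregnancy, and adverse events that in the investigator's judgment "may cause severe or permanent harm or which rule out continuation of study drug". Section 4.3 makes continued therapy conditional on clinical benefit, on no Section 5.5 criterion being met and on no disease progression. Neither section mentions a taper.

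**The concern.** The trigger for the taper is a decision to stop or interrupt drug. Its description, to keep a beneficial dose or go back up to one, reads as guidance for a subject who is staying on treatment. An investigator who follows the text literally could keep a subject on a maintained or higher dose under the name of tapering after a stopping criterion has been met.

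This matters in a study whose main objective is long-term safety and tolerability. Section 4.5 treats the period around withdrawal as hazardous, since it provides for life-threatening events that may follow discontinuation, interruption or reduction of ruxolitinib. Section 5.4 has local physicians supervising care between site visits, with dose changes approved by the study centre. Several clinicians therefore have to read this paragraph the same way. If they do not, subjects stopped for the same reason may be on reduced, unchanged or raised doses when their adverse events are recorded.

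**Working it through.** No sample size, power, event count or error rate is involved, and the plan gives no figure to reproduce. The check is a comparison of the texts in three steps.

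**Step 1: the taper against its own trigger.** The trigger has two branches, discontinue and interrupt. The description has two options, maintain and increase. For discontinuation, neither option ends at zero dose. For interruption, neither option is a pause in dosing. The word taper implies a decrease, and none is described. In a subject stopped for loss of effect, it is also unclear which beneficial dose is to be maintained.

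**Step 2: where the overriding rules settle the matter.**

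| Situation | Direction given | Settled by rules 1 to 3? |
|---|---|---|
| Platelets below 25 x 10^9/L | Rule 2: interrupt | Yes |
| Platelets 25 to 35 x 10^9/L, confirmed | Rule 3: reduce | Yes |
| Any increase | Rule 1: cap of 25 mg BID or 100 mg QD | As a ceiling only |
| Hold for ANC abnormality | End of 4.4: hold for up to two months | No |
| Hold for non-haematologic toxicity | End of 4.4: discontinue if held longer than two months | No |
| Loss of therapeutic effect | 5.5: discontinue | No |
| Harmful adverse event | 5.5: discontinue | No, unless the event is a low platelet count |
| Suspected pregnancy | 5.5: discontinue | No |
| Withdrawal of consent | 5.5: discontinue | No, but a protocol instruction then has doubtful force |
| Loss to follow-up, death | 5.5: discontinue | Not applicable; nothing to taper |

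Of the six criteria in Section 5.5, two leave nothing to taper (6 - 2 = 4). Setting aside withdrawal of consent leaves three (4 - 1 = 3) for which the maintain-or-increase wording has no overriding rule beyond the cap. The two kinds of non-platelet hold in Section 4.4 are in the same position.

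**Step 3: whether Section 4.3 or 5.5 resolves it.** Section 5.5 directs discontinuation, with no exception for a taper and no statement on whether one may come first. Section 4.3 withdraws permission to continue once a criterion is met. Section 4.4 refers to neither. A reader therefore has a discretionary sentence about keeping or raising the dose beside two sections that point to stopping, and no text that orders them.

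**The case against.** The strongest case on the other side is that this is one badly built sentence with little practical effect. The taper is optional: the investigator is asked to consider it, in light of the subject's state and regimen, and Section 4.4 opens by placing management in the subject's best interest. It would be strained to let an optional sentence defeat the mandatory language of Section 5.5. Section 5.5 also does not demand an immediate stop, so a decreasing taper beforehand need not contradict it. All of this stands, and it limits the point to the maintain-or-increase wording. It does not remove the point, because that wording is the only account of the taper that the protocol gives.

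Four stronger readings are tempting, and the documents do not support them.

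- **A conflict with the platelet rules.** A reader might infer that the taper contradicts the interruption in rule 2. The clause directly after the taper paragraph gives rules 1 to 3 precedence, so no conflict remains there.
- **A taper at every stop.** A reader might infer that tapering is recommended whenever drug is stopped or interrupted, and so affects every such subject. It is only to be considered, platelet interruptions are governed by rule 2, and death and loss to follow-up leave nothing to taper.
- **Misassigned safety windows.** A reader might infer that an undefined taper blurs the 30-day periods for serious adverse events and contraception. Section 7 and Section 3.1 already count both from the last dose, so each window moves with the taper. Serious adverse events are captured continuously from the first protocol-specific intervention. The safety sections of Section 8 plan no split between on-treatment and post-treatment events, so there is no period to which an event could be wrongly assigned.
- **A prescribed remedy.** A reader might conclude that the taper must be a step-down, or must be barred for certain stops. That is a clinical choice which the documents do not settle and which is not for this review to make.

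**Conclusion.** The concern holds in limited form. The description of the taper in Section 4.4 contradicts its own trigger and is not reconciled with Sections 4.3 and 5.5. Its reach is three of the six Section 5.5 criteria, plus holds for ANC abnormalities and for non-haematologic toxicity. The count of three sets aside withdrawal of consent; including it makes four. How many subjects would be affected cannot be worked out, because the documents give neither an enrolment figure nor a discontinuation rate.

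No planned summary or table changes. The importance lies in the fact that this is a dosing instruction for subjects coming off drug in a study of long-term safety. The conclusion assumes that the third paragraph of Section 4.4 describes the same strategy that the second recommends. The shared term and the adjacent position support this. If the sponsor meant the maintain-or-increase words for subjects who continue treatment, the text does not say so, and the same clarification is needed.

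**What to change.** The sponsor should reconcile the two taper paragraphs of Section 4.4 with each other and with Sections 4.3 and 5.5. The revised text should state:

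- whether the maintain-or-increase wording applies to subjects who continue treatment or to those being stopped or interrupted;
- how it stands in relation to the Section 5.5 criteria, the condition for continuing in Section 4.3, and the ANC and non-haematologic holds in Section 4.4;
- how it relates to rules 1 to 3.

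The clinical content of the taper is the sponsor's to decide. The cost is a wording amendment, submitted to the IRB as Section 9.1 requires, with no new visits, procedures, data items or analyses.
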